7.0 ADVERSE EVENTS AND POTENTIAL RISKS

7.1 Agent Adverse Events

The most commonly occurring adverse reactions for Decitabine and venetoclax are:

- Nausea
- Reduced red blood count (anemia)
- Low blood platelets count (thrombocytopenia)
- Vomiting
- Raised body temperature; fever
- Reduced white blood cell count (leukopenia)
- Diarrhea
- Weakness
- Reddening of the skin at Injection site (erythema)
- Constipation
- Abnormally low count of white blood cells (neutropenia)
- Discoloration of the skin resulting from bleeding underneath (ecchymosis)
- Round spots that appear on the skin as a result of bleeding (petechia)
- Low potassium level (hypokalemia)
- Shivering as a result of a high fever (rigors)

Leukopenia is a major toxicity of decitabine and nausea, or vomiting were common non-hematologic toxicities. The main side-effect was an increase in the platelet count (as opposed to the usual side-effect of thrombocytopenia seen with cytotoxic treatments) consistent with a non-cytotoxic mechanism of action. Cytotoxicity/DNA damage assays based on bone marrow morphological examination, bone marrow DNA content analysis, VDJ recombination assay,

erythrocyte micronucleus assay and gamma-H2AX assay were also negative. These assays did not reveal evidence of DNA damage or cytotoxicity. The increase in the platelet count was not associated with any clinical adverse events, and specifically, without evidence by correlative studies for an increase in thrombotic tendency.

7.2 Definitions

7.2.1 Adverse Event

An adverse event (AE) is any unfavorable or unintended event, physical or psychological, associated with a research study, which causes harm or injury to a research participant as a result of the participant's involvement in a research study. The event can include clinically significant abnormal laboratory findings, symptoms, or disease associated with the research study. The event does not necessarily have to have a causal relationship with the research, any risk associated with the research, the research intervention, or the research assessments.

Adverse events may be the result of the interventions and interactions used in the research; the collection of identifiable private information in the research; an underlying disease, disorder, or condition of the subject; and/or other circumstances unrelated to the research or any underlying disease, disorder, or condition of the subject

7.2.2 Serious Adverse Events

A **serious adverse event** (SAE) is any adverse experience occurring at any dose that results in any of the following outcomes:

- Results in **death**.
- Is a **life-threatening** adverse experience. The term life-threatening in the definition of serious refers to an adverse event in which the subject was at risk of death at the time of the event. It does not refer to an adverse event which hypothetically might have caused death if it were more severe.
- Requires **inpatient hospitalization or prolongation of existing hospitalization**. Any adverse event leading to hospitalization or prolongation of hospitalization will be considered as Serious, UNLESS at least one of the following expectations is met:
 - The admission results in a hospital stay of less than 24 hours OR
 - The admission is pre-planned (e.g., elective or scheduled surgery arranged prior to the start of the study) OR
 - The admission is not associated with an adverse event (e.g., social hospitalization for purposes of respite care).

However it should be noted that invasive treatment during any hospitalization may fulfill the criteria of “medically important” and as such may be reportable as a serious adverse event dependent on clinical judgment. In addition, where local regulatory authorities specifically require a more stringent definition, the local regulation takes precedent.

- Results in **persistent or significant disability/incapacity**. The definition of disability is a substantial disruption of a person’s ability to conduct normal life’s functions.
- Is a **congenital anomaly/birth defect**.
- Is an **important medical event**. Important medical events that may not result in death, be life-threatening, or require hospitalization may be considered a serious adverse experience when, based upon appropriate medical judgment, they may jeopardize the subject and may require medical or surgical intervention to prevent one of the outcomes listed in this definition. Examples of such medical events include allergic bronchospasm requiring intensive treatment in an emergency room or at home, blood disease or disorders, or convulsions that do not result in inpatient hospitalization, or the development of drug dependency or drug abuse. The development of a new cancer is always considered an important medical event.

Moreover, grade 3 and 4 hematologic laboratory investigations are common in myeloid malignancies and will not be considered SAEs regardless of clinical significance. Grade 3 and 4 laboratory investigations not felt clinically significant by the treating physician will not be considered SAEs.

Patients with hematologic malignancies are known to have high rates of neutropenic fever, admission for the administration of IV antibiotics for uncomplicated neutropenic fever will not be considered a Serious Adverse Event, but will be tabulated as grade 3 or grade 4 toxicity as appropriate.

7.2.3 Adverse Event Evaluation

The investigator or designee is responsible for ensuring that all adverse events (both serious and non-serious) observed by the clinical team or reported by the subject which occur after the subject has signed the informed consent are fully recorded in the subject's medical records. Source documentation must be available to support all adverse events.

Any grade laboratory investigation abnormality considered clinically significant should be reported as an adverse event, with exceptions as noted above.

The investigator or sub-investigator (treating physician if applicable) will provide the following for all adverse events (both serious and non-serious):

- Event term (as per CTCAE)
- Description of the event
- Date of onset and resolution
- **Expectedness of the toxicity**
- **Grade of toxicity**
- **Attribution of relatedness to the investigational agent - (this must be assigned by an investigator, sub-investigator, or treating physician)**
- Action taken as a result of the event, including but not limited to; no changes, dose interrupted, reduced, discontinued, etc. or action taken with regard to the event, i.e. no action, received concomitant medication or other intervention, etc.
- Outcome of event

Descriptions and **grading scales** found in the NCI Common Terminology Criteria for Adverse Events (CTCAE) version **5.0** will be utilized for AE reporting.

An expected adverse event is an event previously known or anticipated to result from participation in the research study or any underlying disease, disorder, or condition of the subject. The event is usually listed in the package insert for Decitabine or venetoclax, consent form or research protocol.

An unexpected adverse event is an adverse event not previously known or anticipated to result from the research study or any underlying disease, disorder, or condition of the subject.

Attribution is the relationship between an adverse event or serious adverse event and the study drug. Attribution will be assigned as follows:

- Definite – The AE is clearly related to Decitabine/venetoclax.
- Probable – The AE is likely related to Decitabine/venetoclax.
- Possible – The AE may be related to Decitabine/venetoclax.
- Unlikely – The AE is doubtfully related to Decitabine/venetoclax.
- Unrelated – The AE is clearly NOT related to Decitabine/venetoclax.

Protocol must specify if attribution is required for individual components of the treatment regimen or the treatment regimen as a whole.

7.3 SAE Report Form

SAEs will be recorded in Velos and reported to the DSMC. If needed, the SAE will also be reported to Einstein IRB

7.4 Reporting Procedures for Serious Adverse Events

For the purposes of safety reporting, all adverse events will be reported that occur on or after day 1 of cycle 1 through 30 days after the final dose of study drug. Adverse events, both serious and non-serious, and deaths that occur during this period will be recorded in the source documents. All SAEs should be monitored until they are resolved or are clearly determined to be due to a subject's stable or chronic condition or intercurrent illness(es). Related AEs will be followed until resolution to baseline or grade 1 or stabilization.

7.4.1 SAE Reporting Requirements

- Participating investigators (all sites) must report all serious adverse events to the Principal Investigator within **24 hours** of discovery or notification of the event. The participating investigator must also provide follow-up information on the SAE until final resolution.

- [name], E-mail: [contact],
[contact]

The Principal Investigator will review the SAE and report the event to the DSMC and IRB as applicable.

It is the Principal Investigator's responsibility to ensure that ALL serious adverse events that occur on the study (e.g. ALL SAEs that occur at each enrolling institution) are reported to all participating sites.

Institutional Review Board Reporting Requirements:

- Principal investigator will report adverse events to the IRB according to the Einstein IRB's policies and procedures in reporting adverse events.

7.5 SAEs and REDcap

- All SAEs will be entered into the REDcap database.
- A copy of the SAE form(s) submitted to the investigator is also uploaded into the REDcap database.

7.6 Data Safety and Toxicity Committee

It is the responsibility of the PI to ensure that all SAEs occurring on this trial are reported to the Einstein's Cancer Center's Data and Safety Toxicity Committee. This submission is simultaneous with their submission to other regulatory bodies.

The principal investigator is responsible for submitting an annual report to the DSTC as per CCCC Data and Safety Monitoring Plan.

- **7.7 Data and Safety Monitoring Plan (DSMP)**

This protocol will adhere to the policies of the Montefiore/Einstein Cancer Center Data and Safety Monitoring Plan in accordance with NCI guidelines. The principal investigator will review with his co-investigators the data relevant to the safety run-in phase, stopping rules (see sections 6.5 and 6.6) and also for an interim analysis. As outlined in sections 6.5 and 6.6, if 3 or more of the first 6 patients develop Grade 3 or 4 non-hematologic, non-infectious toxicity possibly, probably or definitively related to decitabine or venetoclax, during the induction phase (weeks 1-8) of therapy, then the study will be permanently stopped. During the course of the clinical trial, an interim analysis will be done to monitor the safety

following the accrual of every 3 patients after run-in of 6 patients. The stopping criteria are described for the incidence of Grade 3 or 4 non-hematologic, non-infectious toxicity (SAE). Using Bayesian toxicity monitoring with maximum probability of Grade ≥ 3 non-hematologic toxicity of 0.2, prior distribution (1,1), maximum patients 33, minimum number of patients before stopping 3, cohort size 3, and posterior probability 0.8, we will pause the study for review if 2 out of 3, 4 out of 9, 7 out of 18, and 12 out of 33 experience SAEs.

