6.5 Early Stopping Rule for Excessive Toxicity

Bayesian toxicity monitoring (<https://trialedesign.org/one-page-shell.html#BTOX>) will be used to terminate early for excessive toxicity. The maximum allowable probability of Grade ≥ 3 non-hematologic, non-infectious toxicity related to treatment during the induction phase (weeks 1-12) attributed to study treatment, is assumed to be 20% and prior distribution (1,1), then early stopping will occur if the posterior probability that the Grade ≥ 3 non-hematologic toxicity rate exceeds this maximum allowable rate is 80% or greater. The minimum number of patients before stopping 3, cohort size 3, then the study will be stopped early for example, if 2 out of 3, 4 out 9, 7 out of 18, and 12 out of 33 experience SAEs.

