Efficacy: The primary end-point of a decrease in dose interruptions will be described as proportion of patients point-estimates, together with the corresponding 95% confidence interval. Kaplan-Meier method will be used to summarize time to event variables.

Secondary end-points and scientific correlative studies: For the secondary end-points and scientific correlates (secondary objectives), either logistic regression or correlation analysis will be utilized to examine and assess the relationships and predictive nature of these biological parameters on hematologic improvement and ability of decitabine/ven to deplete DNMT1 in malignant cells, and the alteration of pyrimidine metabolism. Descriptive summaries of the data will be provided.

Accrual rate: Estimated accrual rate of 1-3 patients per month with approximately 18-24 months to meet total accrual goals, and additional 3 months to observe primary outcome measures. DOR of response will be followed for up to two years, thus a total of three to four years is anticipated to meet all study endpoints.

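### Toxicity looks are triggered by accrual of every 3 patients while events are counted over a window of up to 12 weeks; with no follow-up condition, recently enrolled patients enter as event-free and stopping comes late

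*Combined protocol and SAP*

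**What the plan says.** - **Timing of looks.** Section 7.7 places the interim safety analyses "following the accrual of every 3 patients after run-in of 6 patients". Its parameters are a maximum "toxicity of 0.2, prior distribution (1,1), maximum patients 33, minimum number of patients before stopping 3, cohort size 3, and posterior probability 0.8".
- **Event window.** Section 6.5 limits Grade 3 or higher non-hematologic, non-infectious "toxicity related to treatment during the induction phase (weeks 1-12) attributed to study treatment, is assumed to be 20" per cent. Section 7.7 gives a different window for the run-in rule: "during the induction phase (weeks 1-8) of therapy, then the study will be permanently stopped".
- **Boundaries.** Sections 6.5 and 7.7 both list 2/3, 4/9, 7/18 and 12/33. Section 6.5 acts when the posterior probability that the "toxicity rate exceeds this maximum allowable rate is 80% or greater". Section 7.7 adds a run-in rule: "if 3 or more of the first 6 patients develop Grade 3 or 4 non-hematologic, non-infectious toxicity".
- **Who counts.** Section 3.2 makes every patient who starts therapy evaluable for safety and sets no minimum follow-up.
- **Pace and reach.** Section 13.0 gives an "Estimated accrual rate of 1-3 patients per month" and continues the Bayesian monitoring into the expansion phase.

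No section requires counted patients to have completed the window, holds accrual before a look, or allows for partial follow-up. Sections 7.7 and 13.0 refer to a section 6.6 that the current body does not contain, so no such condition can be found there either.

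**The concern.** An x-out-of-n toxicity rule has its intended meaning only if each of the n patients has been watched for the whole event window. Here the look is triggered when a patient is enrolled, so the newest patients have had almost no time to show an event, yet each adds one to n. That pulls the posterior down. The rule then has less sensitivity than its 20% limit and 80% posterior suggest, and more patients are treated before it triggers. The effect is greatest at the early looks, which is where a stopping rule protects most.

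**Working it through.** **Inputs.** Limit 0.20, Beta(1,1) prior, cutoff 0.80, cohorts of 3, maximum 33 (sections 6.5 and 7.7). Window W = 12 weeks = 12 × 7 / 30.44 = 2.76 months (6.5), or 8 weeks (7.7 run-in). Accrual 1-3 per month (13.0). Onset timing and the true toxicity rate are not in the documents. I assume uniform onset and mainly a 40% rate.

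**1. The plan's own boundaries.** The boundary is the smallest x with P(p > 0.20 | Beta(1+x, 1+n−x)) ≥ 0.80. This gives 1/3, 3/9, 5/18 and 9/33, not the listed 2/3, 4/9, 7/18 and 12/33. The listed points have posteriors 0.973, 0.967, 0.977 and 0.989. No single cutoff gives all four: 4/9 needs a cutoff of at most 0.967, while excluding 11/33 needs one above 0.973. The documents do not settle which applies, so I carried both. For looks between the listed points I used x = n/3 + 1, which passes through all four and through 3 of 6.

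**2. Patients still inside the window.** With even spacing and n ≥ 9:

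| Window | 1/month | 2/month | 3/month |
|---|---|---|---|
| 12 weeks | 3 | 6 | 9 |
| 8 weeks | 2 | 4 | 6 |

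At 3 per month and 12 weeks, nobody has finished the window at the looks at 3, 6 or 9.

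**3. Events visible at a look.** With uniform onset, the expected number is p × Σ min(t/W, 1), where t is time since enrolment. At 3 per month the last 9 patients contribute (0+1+…+8)/3/2.76 = 4.35 instead of 9. At 1 per month the last 3 contribute (0+1+2)/2.76 = 1.09 instead of 3. With p = 0.40:

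| n | Listed boundary | Complete data | 1/month | 3/month |
|---|---|---|---|---|
| 9 | 4 | 3.6 | 7.09 × 0.4 = 2.8 | 4.35 × 0.4 = 1.7 |
| 18 | 7 | 7.2 | 16.09 × 0.4 = 6.4 | 13.35 × 0.4 = 5.3 |
| 33 | 12 | 13.2 | 31.09 × 0.4 = 12.4 | 28.35 × 0.4 = 11.3 |

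**4. What weighting does at one look.** Take n = 9, 3 per month, and two events, in the 4th and 5th patients enrolled. As written, Beta(3, 8) gives P(p > 0.20) = 0.68, so no action at 0.80. Those two patients have completed fractions 0.60 and 0.48, so the event-free weight is 4.35 − 0.60 − 0.48 = 3.26. Beta(3, 4.26) gives 0.89, so the cutoff is crossed.

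**5. Simulation** (Poisson accrual, uniform onset over 12 weeks, 40% toxicity, maximum 33, scheduled looks only).

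With the 0.80 posterior and looks from patient 3, mean enrolment at stopping is:
- 3 per month: about 15 as written, about 10 weighted.
- 1 per month: 9.6-9.9 as written, 8.3 weighted.

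With the boundary through the listed points, the chance of stopping before patient 33 is:
- Complete data: about 86% with accrual held, or 85%, 83% and 82% at 1, 2 and 3 per month with accrual left open.
- As written: about 74%, 65% and 57-59% at 1, 2 and 3 per month.
- As written with an 8-week window: 77%, 72% and 66%.
- As written with onset skewed early: 76%, 71% and 65%.

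**6. Cost at an acceptable rate** (10% toxicity, 3 per month, 0.80 posterior). With looks from patient 3, trials pause in about 20% weighted against 7% as written. With looks from patient 6, about 20% weighted against 2% as written and 14% with complete data.

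**The case against.** - **The documents never say that pending patients are non-events.** True. A reader might infer that the sponsor chose to score them so, and the text does not support that. It follows from reading an x-out-of-n rule at accrual with every treated patient evaluable. The defect is a missing follow-up condition, but following the plan literally still delays stopping.
- **Much of the lost sensitivity comes from the boundary conflict.** This stands in part. The listed boundaries are harder to cross than 0.80 implies, so the whole shortfall should not be put down to timing. The timing effect appears under either boundary.
- **Complete follow-up would stop after about 5 patients.** A reader might set 15 against 5. The figure of 5 requires accrual to be held until each cohort finishes, which neither the plan nor this fix does. The fair contrast is 15 against 10, and at 1 per month it is under two patients.
- **Behaviour at exactly 20%.** As written the 0.80 rule stops 27-46% of trials there, and weighting raises that above half. Since 20% is the maximum allowable rate, more stopping at that point is not plainly better, and I do not rely on it.
- **Other safeguards exist.** Section 7.4.1 requires SAE reports to the Principal Investigator within 24 hours, and section 6.3 lets the study chair suspend the study. These limit exposure but do not alter the rule's denominator.
- **Early looks are past.** Section 13.0 reports 19 enrolled, 17 evaluable and no safety concerns. That lowers the urgency, and nothing here implies that patients have been harmed. Pending patients are also a smaller share later (9 of 9 at the third look, 9 of 33 at the last, at 3 per month). The rule nevertheless continues into an expansion of up to 85 patients, for which nothing was simulated here.

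**Conclusion.** The point holds, as something the sponsor should correct. Accrual-timed looks without a follow-up condition make the toxicity rule slower than its parameters suggest. The loss is about five patients of mean enrolment at 3 per month, and one to two at 1 per month, under the 0.80 posterior. With the listed boundaries, the chance of stopping at 40% toxicity falls by about 12 percentage points at 1 per month (86% to 74%) and 27-29 at 3 per month (86% to 57-59%). These sizes rest on assumed uniform onset, an assumed 40% rate, a 12-week window and a maximum of 33. The direction was the same with an 8-week window, early-skewed onset, looks from patient 6 and either boundary.

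A reader might also infer that weighting never pauses more often than complete data would. That is not supported: it depends on whether looks start at patient 3 or at 6, and section 7.7 can be read either way. With looks from 6, weighting pauses more often (about 20% against 14% at 10% toxicity and 3 per month).

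**What to change.** 1. Reconcile the passages the rule depends on: weeks 1-8 or weeks 1-12; the listed boundaries or the 0.80 cutoff (which gives 1/3, 3/9, 5/18, 9/33); looks from patient 3 or from patient 6; and stopping (6.5) or pausing for review (7.7).
2. Keep accrual open. At each scheduled look, and whenever a new qualifying event is reported, count each event in full and weight each event-free patient by the fraction of the toxicity window completed (1 once complete). Then apply the reconciled posterior cutoff.
3. Report operating characteristics at 1, 2 and 3 patients per month, including the event-triggered rechecks (not in the simulations above) and the expansion phase. State whether counts carry over from the first 33 patients.

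The work is a short script or spreadsheet plus an amendment to sections 6.5, 7.7 and 13.0. The real cost is the extra pauses for review at an acceptable toxicity rate shown above, and event-triggered rechecks may add some. If the sponsor finds that too many, the cutoff can be chosen with those operating characteristics in view.

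### At the same toxicity counts Section 6.5 stops the study and Section 7.7 pauses it, and both count SAEs although the 20% limit is on related non-hematologic, non-infectious Grade ≥3 toxicity

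*Combined protocol and SAP*

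**What the plan says.** **Limit (Section 6.5).** The rule starts from "The maximum allowable probability of Grade ≥ 3 non-hematologic, non-infectious toxicity related to treatment during the induction phase (weeks 1-12"), set at 20% with a (1,1) prior. Action follows when "the posterior probability that the Grade ≥ 3 non-hematologic toxicity rate exceeds this maximum allowable rate" with probability at least 0.80.

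**Counts and action in 6.5.** The text continues "then the study will be stopped early for example, if 2 out of 3" and ends its list with "12 out of 33 experience SAEs".

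**Counts and action in 7.7.** The settings are the same, with "maximum patients 33, minimum number of patients before stopping 3, cohort size 3", but the instruction is to "pause the study for review if 2 out of 3, 4 out of 9, 7 out of 18, and 12 out of 33 experience SAEs". The preceding sentence reads "The stopping criteria are described for the incidence of Grade 3 or 4 non-hematologic, non-infectious toxicity (SAE"), which attaches the abbreviation to the toxicity.

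**Meaning of SAE (7.2.1-7.2.2).** An SAE is defined by outcome: death, threat to life, admission and so on. An adverse event need not be caused by the treatment. Admissions count, with exceptions such as stays under 24 hours. Hematologic laboratory values, laboratory values the physician considers not clinically significant, and admissions for IV antibiotics for uncomplicated neutropenic fever are not SAEs. Other infections are not excluded.

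**Expansion (Section 13).** The Bayesian monitoring continues in the expansion by reference to Section 6.6, which appears in the contents but not in the body. No counts are listed beyond 33, while enrolment may reach 85.

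**The concern.** This rule protects patients, and two parts of it must be settled before a boundary is reached: what is counted, and what happens then.

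**Action.** Stopping early and pausing for review differ in whether the study can resume. An investigator at a boundary holds two instructions from one protocol and no statement of which prevails.

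**Event.** The set the limit governs and the set the counts name overlap, but neither contains the other. An unrelated admission, or a pneumonia admission of more than 24 hours, is an SAE but not the limited toxicity. Section 6.1.5 calls infections common in these patients, and Section 2.2 makes infection admission a secondary endpoint, so such events are to be expected. In the other direction, a related Grade 3 toxicity handled as Table 1 directs (hold, then restart at a 25% reduction) with no serious outcome is the limited toxicity but not an SAE. A literal count could therefore trigger the rule on events that the limit excludes, or miss events that it is meant to catch.

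**Working it through.** **1. The plan's own counts.** Inputs from 6.5: limit 0.20, prior Beta(1,1), cutoff 0.80. With x events in n patients, the posterior probability that the rate exceeds 0.20 is the upper tail of Beta(1+x, 1+n−x) beyond 0.20.

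| Listed count | Posterior | Smallest count reaching 0.80 | Posterior there |
|---|---|---|---|
| 2/3 | 0.973 | 1/3 | 0.819 |
| 4/9 | 0.967 | 3/9 | 0.879 |
| 7/18 | 0.977 | 5/18 | 0.837 |
| 12/33 | 0.989 | 9/33 | 0.875 |

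The listed counts are higher than the stated criterion requires. That is a separate question. The examples below are chosen so that the listed count and the posterior criterion agree within each row.

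**2. Event, worked at 33 patients (listed boundary 12).** A monitored event is the toxicity as 6.5 limits it. SAE is read as in 7.2.2, with one count per patient.

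| Case | Counted as | x | Posterior | Result |
|---|---|---|---|---|
| A: 4 serious monitored events, plus 8 other patients admitted with pneumonia | Monitored events | 4 | 0.162 | Continue |
| A | SAEs (4 + 8) | 12 | 0.989 | Boundary met |
| B: 12 monitored events, 5 of them serious, no other SAEs | Monitored events | 12 | 0.989 | Boundary met |
| B | SAEs | 5 | 0.300 | Continue |

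The case mixes are illustrative, because the documents give no SAE rates. The pneumonia admissions are taken to last at least 24 hours and not to be uncomplicated neutropenic fever.

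**3. Event wording, side by side.**

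| Place | Grade | Non-infectious | Related | Window |
|---|---|---|---|---|
| 6.5, limit | ≥3 | Yes | Yes | Weeks 1-12 |
| 6.5, posterior sentence | ≥3 | Not stated | Not stated | Not stated |
| 6.5, counts | SAEs | – | – | – |
| 7.7, sentence introducing the stopping criteria | 3 or 4 | Yes | Not stated | Not stated |
| 7.7, Bayesian settings | ≥3 | Not stated | Not stated | Not stated |
| 7.7, counts | SAEs | – | – | – |

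**4. Action, side by side.** At 2/3, 4/9, 7/18 and 12/33, 6.5 stops early and 7.7 pauses for review. Section 13 speaks of allowing early stopping, which fits either a direct stop or a pause followed by a decision.

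**5. Reach.** The expansion adds up to 85 − 33 = 52 patients. With no listed counts there, only the posterior criterion can operate, and its sentence is worded on toxicity.

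**The case against.** The strongest reply is that the text largely settles the event. Section 7.7 labels the toxicity SAE just before using that word in its counts. In 6.5 both the limit and the posterior sentence are stated in toxicity terms, the posterior sentence points back to the limit just defined, and SAEs appear only in counts offered as examples. On that view SAE is loose shorthand.

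Much of this stands: shorthand is the more natural reading of 7.7. It does not cure the defect, because 6.5 carries no such label and 7.2.2 gives the term a different formal meaning, which sites will use when they report SAEs. It also does nothing for stop versus pause.

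A second reply also has force. The exclusion of uncomplicated neutropenic fever removes a foreseeable class of infection admissions from any SAE count. Pneumonia and sepsis admissions remain.

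A reader might go further and infer that SAE counting would drive the rule throughout the expansion, with a calculable chance of a wrongful or missed stop. The documents do not support that. After 33 patients no SAE count is listed, the posterior criterion is worded on toxicity, and any such probability would rest on SAE rates that the documents do not give.

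**Conclusion.** The point holds on the current text, in two parts.

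The action conflict is unqualified: identical counts, two instructions, and nothing that reconciles them. Both do interrupt the study at the boundary, so the difference is whether review can lead to resumption.

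The event conflict holds for the listed counts up to 33. Cases A and B show that the choice of event can reverse the answer in either direction. They show what can happen, not how likely it is. In the expansion the event defect is narrower: the posterior sentence omits the non-infectious, relatedness and window terms that the limit contains.

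Two further readings should not be drawn from this point. The gap between the listed counts and the 20% limit is a separate matter, and nothing here depends on how it is settled. The 3-of-6 run-in rule in 7.7, with its "during the induction phase (weeks 1-8) of therapy, then the study will be permanently stopped", conflicts with the 12-week induction used elsewhere and does not appear in 6.5. It is evidently past, since Section 13 reports 19 enrolled and 17 evaluable after induction, so it is clean-up. The Section 6.6 citation looks like a renumbering slip.

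**What to change.** 1. In 6.5, define one monitored event: Grade ≥3 (including Grade 5) non-hematologic, non-infectious toxicity that is possibly, probably or definitely related to decitabine or venetoclax, in weeks 1-12, with each patient counted once regardless of SAE status.
2. Use that term in the posterior sentence of 6.5, in 7.7 and in Section 13. It replaces the SAE wording in both lists of counts, the parenthetical SAE label in 7.7, and the Grade 3 or 4 wording there.
3. State one action in both sections: stop, or pause pending review. The sponsor must choose.
4. In Section 13, state that the posterior criterion continues on the monitored event every 3 patients up to 85. Add the counts once the separate question about the listed counts is settled.
5. Clean-up: point the Section 6.6 references in 7.7 and 13 to 6.5, and either declare the run-in rule complete or correct its window to weeks 1-12.

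The cost is a wording amendment and one decision. Section 7.2.3 already requires grade, attribution and onset date for every adverse event, so no new data or patients are needed.
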